11.1.4 Serious Adverse Events or Serious Drug Reactions

A serious adverse event (SAE) or serious adverse drug reaction (SADR) is any untoward medical occurrence that at any dose:

- results in death
- is life-threatening
NOTE: The term “life-threatening” in the definition of “serious” refers to an event in which the participant was at risk of death at the time of the event; it does not refer to an event/reaction that hypothetically might have caused death if it were more severe.
- requires inpatient hospitalization or prolongation of existing hospitalization
NOTE: Inpatient hospitalization is defined as 24 hours in a hospital or an overnight stay. An elective hospital admission to treat a condition present before exposure to the IP, or a hospital admission for a diagnostic evaluation of an AE, does not qualify the condition or event as an SAE. Further, an overnight stay in the hospital that is only due to transportation, organization, or accommodation problems and without medical background does not need to be considered an SAE.
- results in persistent or significant disability/incapacity
- is a congenital anomaly
NOTE: A congenital anomaly in an infant born to a mother who was exposed to the IP during pregnancy is an SAE. However, a newly diagnosed pregnancy in a participant that has received an IP is not considered an SAE unless it is suspected that the IP(s) interacted with a contraceptive method and led to the pregnancy.
- is an important medical event
NOTE: Medical and scientific judgment should be exercised in deciding whether other situations should be considered serious, such as important medical events that might not be immediately life-threatening or result in death or hospitalization but might jeopardize the participant or might require intervention to prevent one of the other outcomes listed in the definition above. Examples of such events are intensive treatment in an emergency room or at home for allergic bronchospasm, blood dyscrasias, or convulsions that do not result in hospitalization, or development of drug dependency, or drug abuse. The occurrence of malignant tumors is also to be considered serious.

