5.4. Summary of Potential Risks and Benefits

The potential benefits of study participation are that participants with VVA may experience a reduction in the symptoms associated with VVA as a result of treatment with DARE-VVA1. No other benefits of participation are anticipated.

The potential risks of study participation include those associated with exposure to tamoxifen and the excipients found in DARE-VVA1 and the risks of medical evaluation, including venipuncture.

Oral tamoxifen (tablets or solution) is approved for the treatment of estrogen receptor-positive metastatic breast cancer and to reduce the risk of breast cancer in women at high risk.¹⁸ The label includes a boxed warning concerning the risk of uterine malignancies, stroke, and pulmonary embolism. General warnings include risks of thromboembolic events (although this risk is greater when co-administered with chemotherapy), embryo-fetal toxicity (which is not a risk in the present study population), and liver cancer and liver abnormalities.

The National Surgical Adjuvant Breast and Bowel Project reported relative risks of serious events in a double-blind, placebo-controlled study of 5 years' treatment with tamoxifen (20 mg per day) designed to evaluate whether treatment would reduce the incidence of invasive breast cancer in high-risk women. After a median treatment duration of 3.5 years in 13,388 women, the rates (per 1,000 women per year) for major outcomes were as follows:

Major Outcomes	Rates for tamoxifen (per 1,000 women per year)	Rates for placebo (per 1,000 women per year)
Endometrial adenocarcinoma	2.20	0.71
Uterine sarcoma	0.17	0.0
Stroke	1.43	1.00
Pulmonary emboli	0.75	0.25
Deep vein thrombosis	1.26	0.79
Cataracts	25.41	22.51

Source: Soltamox label¹⁸

In addition to these serious risks, the most common adverse reactions with oral tamoxifen include hot flashes, mood disturbances, vaginal discharge, vaginal bleeding, nausea, and fluid retention.¹⁸

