11.2. Event Assessment and Follow-up of Adverse Events

The occurrence of an AE or SAE may come to the attention of study personnel during study visits and interviews of a study participant presenting for medical care or upon review by a study monitor.

All AEs including local and systemic reactions not meeting the criteria for SAEs will be captured on the appropriate eCRF. Information to be collected includes event description, time of onset, clinician's assessment of severity, relationship to study product (assessed only by those with the training and authority to make a diagnosis), and time of resolution/stabilization of the event. All AEs occurring while on study must be documented appropriately regardless of relationship. All AEs will be followed to adequate resolution.

Any medical condition that is present at the time that the participant is screened will be considered as baseline and not reported as an AE. However, if the study participant's condition deteriorates at any time during the study, it will be recorded as an AE.

Changes in the severity of an AE will be documented to allow an assessment of the duration of the event at each level of severity to be performed. Any AEs characterized as intermittent require documentation of onset and duration of each episode.

The investigator (or designee) will record all reportable events with start dates occurring any time after informed consent is obtained until 7 (for nonserious AEs) or 30 days (for SAEs) after the last day of study participation. At each study visit, the investigator will inquire about the occurrence of AE/SAEs since the last visit. Events will be followed for outcome information until resolution or stabilization.

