11.2.6 Reporting

11.2.6.1 Serious Adverse Events

In the event of any SAE reported or observed during the study, whether or not attributable to the study drug, site personnel will report the event to ICON (ICON plc Pharmacovigilance) by email within 24 hours of notification of event in accordance with procedures described in the Study Reference Manual and/or SAE Study Specific Procedure. Site personnel will follow up with a written report to the sponsor on the next working day.

SAE Report Forms will be provided to the clinical research unit to assist in collecting, organizing, and reporting SAEs and follow-up information.

All SAEs should be followed to their resolution, with documentation provided to the sponsor, medical monitor, and ICON on a follow-up SAE Report Form.

At the time of first notification, the investigator or designee should provide the following information, if available:

- Protocol number
- Reporter (study site and investigator)
- Suspect IP
- Participant's study number
- Participant's year of birth
- Participant's gender
- Date of first dose of IP
- Date of last dose of IP, if applicable

- Adverse event term
- Date of occurrence of the event
- A brief description of the event, outcome to date, and any actions taken
- The seriousness criteria(on) that were met
- Concomitant medication at onset of the event
- Relevant medical history information
- Relevant laboratory test findings
- Investigator's opinion of the relationship to IP ("Is there a reasonable possibility that the IP caused the SAE? Yes or No?")
- Whether and when the investigator was unblinded as to the participant's treatment assignment

Any missing or additional relevant follow-up information concerning the SAE should be sent to ICON (ICON plc Pharmacovigilance) as soon as possible with the following minimal information (initial report, adverse event, date of occurrence, participant identification, study number, IP, and site number); this will allow the follow-up information to be linked to the initial SAE report.

Specific information may be requested by ICON plc Pharmacovigilance using a follow-up request form or via email communication.

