12. DATA SAFETY MONITORING BOARD

A data safety monitoring board will not be used in this study.

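### The SAE hospitalization criterion exempts any admission to evaluate an adverse event, so an unplanned overnight work-up of a new event is serious only if another criterion is judged to apply

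*Combined protocol and SAP*

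**What the plan says.** Section 11.1.4 lists alternative seriousness criteria: death, threat to life, inpatient hospitalization or its prolongation, disability, congenital anomaly and important medical event. Under the hospitalization criterion, "Inpatient hospitalization is defined as 24 hours in a hospital or an overnight stay". The same note contains three exemptions:

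- elective admission to treat a condition present before exposure to the product;
- admission for diagnostic evaluation of an adverse event: "or a hospital admission for a diagnostic evaluation of an AE, does not qualify the condition or event as an SAE";
- an overnight stay due only to transport, organization or accommodation, with no medical reason.

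The important-medical-event criterion is left to judgment. It covers events that "might jeopardize the participant or might require intervention to prevent one of the other outcomes listed in the definition above". That note ends with a fixed rule: "The occurrence of malignant tumors is also to be considered serious".

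Seriousness decides how an event is handled. SAEs are reported "by email within 24 hours of notification of event" (section 11.2.6.1). The investigator and the sponsor each assess their relationship to the product (section 11.2.2.5), and they have their own summaries (section 13.1.4.1). Nonserious events go to the eCRF and a safety management plan (section 11.2.6.3), with no reporting clock in the protocol. Under section 11.2, events are recorded by start date, from consent "until 7 (for nonserious AEs) or 30 days (for SAEs) after the last day of study participation".

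Section 5.4 says of oral tamoxifen: "The label includes a boxed warning concerning the risk of uterine malignancies, stroke, and pulmonary embolism". It also names deep vein thrombosis and liver abnormalities as risks, and vaginal bleeding as a common reaction. Section 12 states: "A data safety monitoring board will not be used in this study". Section 13.1.7 plans no interim analysis.

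**The concern.** The first and third exemptions cover admissions that a new event did not cause. The second is different: by its wording it applies to an adverse event, and nothing restricts it to planned admissions or to conditions that predate the study. It therefore takes in an unplanned overnight stay prompted by a new sign or symptom during treatment.

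Some of the risks named in section 5.4 could first appear in this way, before any diagnosis is made. If the site classes the event as nonserious, the report no longer has a 24-hour clock and the event does not count in the SAE tables. Safety is a primary objective, the product has not been given to humans before (section 5.3), and there is no monitoring board or interim look. Prompt and consistent classification by the sites therefore carries more weight than usual.

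**Working it through.** No sample-size or power figure is involved. The check is a comparison of sections plus day arithmetic.

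**1. Which events are exposed**

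| Situation, with an overnight stay for evaluation | Hospitalization criterion | Other route to serious in 11.1.4 |
|---|---|---|
| Malignant tumor found | Exempted | Always serious |
| Confirmed embolism or stroke | Exempted if the stay was for evaluation | Probably life-threatening or important medical event |
| Suspected embolism, unconfirmed, pending or negative | Exempted | Investigator judgment only |
| Resolved TIA | Exempted | Investigator judgment only |
| Uterine bleeding, no malignant finding | Exempted | Investigator judgment only |
| Raised liver enzymes | Exempted | Investigator judgment only |

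The examples under important medical event name no thromboembolic, cerebrovascular or uterine event. The life-threatening note excludes events that would have threatened life only had they been more severe. The last four rows are the exposed cases.

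**2. Recording windows for a completer**

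- Last dose on Day 56; follow-up visit on Day 56 + 7 = Day 63 (section 10.2.4). Check on the timeline: 21 + 56 + 7 = 84 days = 12 weeks, as section 10.1.1 states.
- Nonserious events under section 11.2: Day 63 + 7 = Day 70.
- SAEs under section 11.2: Day 63 + 30 = Day 93.
- Start dates recorded only if serious: Days 71 to 93, which is 93 − 70 = 23 days. With the ±1 day visit window this becomes Days 70 to 92 or 72 to 94, still 23 days.
- Treatment-emergent window (sections 11.1.6 and 13.1.4.1): Day 56 + 30 = Day 86. So 86 − 70 = 16 of the 23 days lie in a period whose events the protocol means to count as treatment-emergent.
- Section 7.1 ends documentation of all adverse events at the follow-up visit. On that reading the gap would begin on Day 64.

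**3. What still catches a late nonserious event**

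Section 11.2.6.2 sends all adverse drug reactions to the eCRF without stating a window. Section 11.1.2 makes a relationship of possibly related enough, and treats a missing relationship as possible. The duty in 11.2.6.2 to report however late covers only suspected reactions already classed as serious. What is left uncaught is a nonserious event that starts on Days 71 to 93 and is rated unlikely related or not related.

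**4. Scale, as an illustration only**

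Assume that the oral 20 mg/day rates in section 5.4 apply to the 4 × 8 = 32 women on active product.

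- Stroke + pulmonary emboli + deep vein thrombosis: 1.43 + 0.75 + 1.26 = 3.44 per 1,000 women per year.
- Days 1 to 93: 32 × 93 / 365.25 = 8.15 woman-years; 8.15 × 0.00344 = 0.028 expected events.
- The 23-day gap: 32 × 23 / 365.25 = 2.02 woman-years; 2.02 × 0.00344 = 0.007 expected events.

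These are diagnosed events, most of which would qualify as serious anyway. The documents give no rate for suspected events, bleeding work-ups or diagnostic admissions, so the number of exposed cases cannot be estimated. In an arm of 8, one reclassified event moves the SAE proportion by 1/8 = 12.5 percentage points; that reflects only the arm size.

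**The case against.** **The criteria are alternatives.** The note sits under hospitalization and can be read as saying only that such an admission is not sufficient by itself. Nothing in it bars another criterion, and an admission to treat an event is not one for evaluation. This stands. A reader might infer that the clause removes the tamoxifen-type events from SAE reporting, but the documents do not support that: malignancy is always serious, and a confirmed embolism or stroke would probably qualify. The objection does not reach unconfirmed or negative work-ups, TIA, or bleeding and enzyme admissions. For these the one objective criterion is switched off and only judgment remains.

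**SAE reporting is not the only safeguard.** A reader might infer that it is the sole early-warning channel, or that only SAEs are followed to resolution. Neither is supported. Sections 11.2 and 11.2.5 follow all adverse events. Section 8.2 brings in the medical monitor when a participant develops an exclusion criterion, and those criteria include thromboembolic disease, TIA and endometrial pathology. Section 8.5 requires prompt notice to the sponsor and medical monitor on withdrawal. Section 10.3.1.1.3 requires clinically relevant laboratory changes to be reported as adverse events. SAE reporting is, however, the only route for which the protocol states a 24-hour clock.

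**Late events are not simply lost.** A reader might infer that a diagnostic admission on Days 71 to 93 would not be recorded at all. Section 11.2 turns on the start date of the event, so an admission in that period for an event that began by Day 70 is still recorded, and 11.2.6.2 catches those rated at least possibly related. The differing windows are also a wider inconsistency that affects every nonserious event. These points stand and narrow the late gap.

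**Unseen documents.** The safety management plan, the Study Reference Manual and any SAE procedure are not available and might add a faster route. That limits certainty about actual delay, but not about what 11.1.4 says.

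**Conclusion.** The concern holds in a limited form. As written, 11.1.4 lets an unplanned overnight admission for a new on-study event fail the hospitalization criterion because its purpose was diagnostic. The event is then serious only if the investigator finds another criterion met. If it is not, the 24-hour report, the sponsor's separate causality assessment and inclusion in the SAE tables are lost, and the recording window is 7 days instead of 30 after the last day of participation.

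Complete loss of the record is confined to nonserious events that start on Days 71 to 93 in a completer and are not considered at least possibly related. This assumes that section 11.2 governs the window and that the last day of participation is Day 63.

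Few such events are expected in 40 women, and their frequency cannot be derived from the documents. The case for change rests on the clarity of safety reporting in a first human study, not on a measurable effect on the results. It should be corrected; it does not threaten the study's validity.

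**What to change.** In section 11.1.4:

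- delete the exemption for admission for diagnostic evaluation of an adverse event;
- keep the exemptions for elective admission for a pre-existing condition and for stays with no medical reason;
- add that an unplanned overnight stay prompted by a new or worsened sign or symptom meets the hospitalization criterion.

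Mirror this in the SAE form instructions. In the same amendment, reconcile the adverse-event windows in sections 7.1, 11.1.6, 11.2 and 11.2.6.2 so that one recording period applies and covers the treatment-emergent definition.

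For a completer, an admission of this kind would then be reported within 24 hours and recorded if the event starts by Day 93. The cost is one clause and one added sentence in 11.1.4, the matching instruction and the alignment of the windows, plus a few more SAE reports, some of which will prove benign. The change to 11.1.4 affects no eligibility criterion, dosing, visit or planned analysis.

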11.1.5 Significant Adverse Events

Other significant AEs are defined as marked hematological and other laboratory abnormalities (other than those meeting the definition of serious) and any events that led to an intervention, including withdrawal of test drug, dose reduction, or significant additional concomitant therapy.

11.1.6 Treatment-emergent Adverse Events

An AE is defined as treatment emergent if the first onset or worsening is after the first administration of IP (DARE-VVA1 or placebo) and not more than 30 days after the last administration of IP.

11.2. Event Assessment and Follow-up of Adverse Events

The occurrence of an AE or SAE may come to the attention of study personnel during study visits and interviews of a study participant presenting for medical care or upon review by a study monitor.

All AEs including local and systemic reactions not meeting the criteria for SAEs will be captured on the appropriate eCRF. Information to be collected includes event description, time of onset, clinician's assessment of severity, relationship to study product (assessed only by those with the training and authority to make a diagnosis), and time of resolution/stabilization of the event. All AEs occurring while on study must be documented appropriately regardless of relationship. All AEs will be followed to adequate resolution.

Any medical condition that is present at the time that the participant is screened will be considered as baseline and not reported as an AE. However, if the study participant's condition deteriorates at any time during the study, it will be recorded as an AE.

Changes in the severity of an AE will be documented to allow an assessment of the duration of the event at each level of severity to be performed. Any AEs characterized as intermittent require documentation of onset and duration of each episode.

The investigator (or designee) will record all reportable events with start dates occurring any time after informed consent is obtained until 7 (for nonserious AEs) or 30 days (for SAEs) after the last day of study participation. At each study visit, the investigator will inquire about the occurrence of AE/SAEs since the last visit. Events will be followed for outcome information until resolution or stabilization.

11.2.1 Assessment

The investigator is responsible for the detection and documentation of events meeting the criteria and definition of an AE or SAE described previously. At each visit, the participant will be allowed time to spontaneously report any issues since the last visit or evaluation. The investigator will then monitor and/or ask about or evaluate AEs using nonleading questions, such as

- “How are you feeling?”
- “Have you experienced any issues since your last visit?”
- “Have you taken any new medications since your last visit?”

Any clinically relevant observations made during the visit will also be considered AEs.

11.2.2 Evaluation

11.2.2.1 Severity of Adverse Events

The clinical severity of an AE will be graded according to the following definitions:

- Grade 1: Mild; the participant experiences awareness of signs or symptoms but these are easily tolerated or managed without specific treatment
- Grade 2: Moderate; the participant experiences discomfort enough to cause interference with usual activity, and/or the condition requires specific treatment

- Grade 3: Severe; the participant is incapacitated with inability to work or do usual activity, and/or the event requires significant treatment measures
- Grade 4: Disabling or with life-threatening consequences, urgent intervention indicated
- Grade 5: Death

It is important to distinguish between severe AEs and SAEs. Severity is a classification of intensity whereas an SAE is an AE that meets serious criteria, as described in Section 11.1.4.

11.2.2.2 Seriousness

The investigator is to evaluate whether the AE meets serious criteria, as described in Section 11.1.4.

11.2.2.3 Actions Taken

Actions taken may consist of:

Dose not changed	An indication that a medication schedule was maintained.
Drug interrupted	An indication that a medication schedule was modified by temporarily terminating a prescribed regimen of medication.
Drug withdrawn	An indication that a medication schedule was modified through termination of a prescribed regimen of medication.
Not applicable	Determination of a value is not relevant in the current context.
Unknown	Not known, not observed, not recorded, or refused.

11.2.2.4 Outcome at the Time of Last Observation

The outcome at the time of last observation will be classified as:

- Recovered/resolved
- Recovered/resolved with sequelae
- Recovering/resolving
- Not recovered/not resolved
- Fatal*
- Unknown

*Investigators should only select fatal as an outcome when the AE results in death. If more than one AE is judged to be possibly related to the participant's death, the outcome of death should be indicated for each such AE. Although "fatal" is usually an event outcome, events such as sudden death or unexplained death should be reported as SAEs.

11.2.2.5 Adverse Event Relationship to Investigational Product

The investigator must make an assessment of each AE's relationship to the IP. The categories for classifying the investigator's opinion of the relationship are as follows:

Not related	The event is most likely produced by other factors such as the participant's clinical condition, intercurrent illness, or concomitant drugs, and does not follow a known response pattern to the study drug, or the temporal relationship of the event to study drug administration makes a causal relationship unlikely
Unlikely related	The event is most likely produced by other factors such as the participant's clinical condition, therapeutic interventions, or concomitant drugs administered to the participant, and it does not follow a known response pattern to the study drug
Possibly related	The event follows a reasonable temporal sequence from the time of drug administration, and/or follows a known response pattern to the study drug, but could have been produced by other factors such as the participant's clinical condition, intercurrent illness, or concomitant drugs
Related	The event follows a reasonable temporal sequence from the time of drug administration, and/or follows a known response pattern to the study drug, and cannot be reasonably explained by other factors such as the participant's clinical condition, intercurrent illness, or concomitant drugs

For SAEs, the event relationship to the IP must be assessed separately by the investigator and Daré.

